20 PUBLICATION POLICY

This clinical investigation will be prospectively registered at a public clinical trial registry,

ClinicalTrials.gov.

A joint peer-reviewed publication authored by the clinical investigator(s) and Sponsor will be prepared. In addition, the results of the clinical investigation may also be disseminated as conference presentations (e.g., abstract and poster session). Manuscript authorship and responsibilities will be discussed and agreed upon prior to investigation start and in accordance with guidelines and recommendations provided by the International Committee of Medical Journal Editors (ICMJE) to enable communication in a timely manner. All contributors who do not meet the criteria for authorship will be listed in an acknowledgments section of the publication.

21 STATEMENTS OF COMPLIANCE

This clinical investigation shall be conducted in accordance with ethical principles that have their origin in the Declaration of Helsinki, International Standard ISO 14155 Clinical investigation of medical devices for human subjects - Good Clinical Practice, and any regional or national regulations, as applicable.

22 QUALITY CONTROL AND ASSURANCE

In accordance with Cochlear's Quality Management System, all clinical investigations shall be conducted according to internationally recognized ethical principles for the purposes of obtaining clinical safety and performance data about medical devices.

The Sponsor employees (or designee) shall use standard operating procedures (SOP) to ensure that clinical study procedures and documentation are consistently conducted and compliant with the ISO 14155 Standard, Good Clinical Practice (GCP), and applicable local regulations.

22.1 Monitoring

The Sponsor will perform on-site and remote monitoring visits as frequently as necessary to oversee conduct, data collection and record keeping by sites. The clinical investigation monitoring plan is a separate document describing all the activities performed during site qualification, initiation, monitoring, and close out.

22.2 Audits

An Investigator must, in reasonable time, upon request from a relevant health authority or regulatory agency, permit access to requested records and reports, and copy and verify any records or reports made by the Investigator. Upon notification of a visit by a regulatory authority, the Investigator will contact the Sponsor immediately.

The Investigator will grant the Sponsor representatives the same access privileges offered to relevant health authority or regulatory agents, officers, and employees.

23 TRADEMARKS AND COPYRIGHT

ACE, Advance Off-Stylet, AOS, AutoNRT, Autosensitivity, Beam, Button, CareYourWay, Carina, Cochlear, 科利耳, コクレア, Cochlear SoftWear, Codacs, ConnectYourWay, Contour, Contour Advance, Custom Sound, ESPrit, Freedom, Hear now. And always, HearYourWay, Hugfit, Hybrid, Invisible Hearing, Kanso, MET, MicroDrive, MP3000, myCochlear, mySmartSound, NRT, Nucleus, Off-Stylet, Slimline, SmartSound, Softip, SPrint, True Wireless, the elliptical logo, WearYourWay and Whisper are either trademarks or registered trademarks of Cochlear Limited. Ardium, Baha, Baha SoftWear, BCDrive, DermaLock, EveryWear, Vistafix, and WindShield are either trademarks or registered trademarks of Cochlear Bone Anchored Solutions AB. © Cochlear 2019

25 CHANGE HISTORY

Version	Change	Rationale
1.0	First draft of document	New Study
2.0	Changes to audiometric thresholds	To align with current FDA-approved indications for the Osia 2 Implant system
3.0	Changes throughout document to remove Cohort 2 (this includes updated inclusion criteria, endpoints, objectives, assessments, and analysis as a result of removal of Cohort 2)	Change to the study design was deemed necessary

6.11	Protocol Deviations	13
7	Changes from Planned Analyses.....	13
8	Subject Listings	13

Statistical Analysis Plan		Page 6 of 13
Sponsor Cochlear Americas	Study A post-market interventional cohort study evaluating the clinical efficacy of the Osia 2 system in the US Market	Version 3.0

1 Introduction

This statistical analysis plan (SAP) describes the planned statistical methods to be used during the reporting and analysis of data collected under the Clinical Investigation Protocol; A post-market interventional cohort study evaluating the clinical efficacy of the Osia 2 system in the US Market. This SAP should be read in conjunction with the study clinical investigation plan (CIP) and case report forms (CRFs). This version of the SAP has been developed with respect to the Clinical Investigation Protocol A post-market interventional cohort study evaluating the clinical efficacy of the Osia 2 system in the US Market, Version 3.0 June 19, 2020. Any revisions to the protocol or CRFs that impact the planned analyses may require updates to the SAP.

2 Abbreviations

Abbreviation/Term	Definition
ADE	Adverse Device Effect
AE	Adverse Event
CIP	Clinical Investigation Plan
CRF	Case Report Form
DD	Device Deficiency
eCRF	Electronic Case Report Form
SADE	Serious Adverse Device Effect
SAE	Serious Adverse Event
SAP	Statistical Analysis Plan
UADE	Unanticipated Adverse Device Effect
USADE	Unanticipated Serious Adverse Device Effect

3 Study Objectives

3.1 Primary Objective

The primary study objective is to evaluate the performance of the Osia 2 system on an adaptive speech in noise test.

Statistical Analysis Plan		Page 7 of 13
Sponsor Cochlear Americas	Study A post-market interventional cohort study evaluating the clinical efficacy of the Osia 2 system in the US Market	Version 3.0

3.2 Secondary Objective

To evaluate the safety of the Osia 2 system in a group of adult newly implanted recipients.

3.3 Study Endpoints

There is one primary endpoint and one secondary endpoint.

The primary endpoint is to demonstrate a significant difference between the aided and unaided conditions in Cohort 1 at 3 months using an adaptive speech in noise test when compared to the preoperative (Visit 1) unaided condition.

The secondary endpoint is to evaluate the safety of the Osia 2 system in a group of adult newly implanted recipients by estimating the incidence of device or procedure related adverse events.

4 Study Design

The study is a prospective interventional cohort study which consists of subjects implanted with the Osia 2 system.

4.1 Randomization

Test order for the 3-month interval will be randomly assigned in a 1:1 allocation ratio, stratified by site. Test order will be either aided followed by unaided, or unaided followed by aided.

4.2 Blinding

Blinding is not planned for this study due to feasibility concerns; specifically, the inability to conceal the presence or absence of the device from recipients or clinical investigators.

4.3 Study Assessments

The statistical analyses for the primary objective will be based on the 3-month assessment compared to the pre-operative baseline assessment. Analyses for the secondary objective will be based on safety data collected at the time of treatment and for the duration of the study up to and including 6 months.

Statistical Analysis Plan		Page 8 of 13
Sponsor Cochlear Americas	Study A post-market interventional cohort study evaluating the clinical efficacy of the Osia 2 system in the US Market	Version 3.0

5 Sample Size Determination

The planned sample size of 20 will provide greater than 80% power under a conservatively assumed mean of 12 and standard deviation of 15. Calculations are based on a one-sided 0.025 alpha and include allowance for attrition of up to 20%.

The primary objective is to evaluate the performance of the Osia 2 system on an adaptive speech in noise test. A paired t-test of superiority for the adaptive speech in noise test, comparing the aided and unaided conditions at 3-months relative to the preoperative (Visit 1) unaided condition. The mathematical statement of this hypothesis test is written as:

$$H_0: \Delta On \geq \Delta Off$$

$$H_1: \Delta On < \Delta Off$$

where ΔOn is the mean change in the adaptive speech in noise test between the 3-month aided (On) condition and the preoperative (Visit 1) unaided condition, and ΔOff is the mean change in the adaptive speech in noise test between the 3-month unaided condition (Off) and the preoperative (Visit 1) unaided condition. Successful rejection of the null hypothesis indicates the aided performance of the Osia 2 system is superior to the unaided performance based on the adaptive speech in noise test.

The secondary objective is to evaluate the safety of the Osia 2 system in a group of adult newly implanted recipients. Descriptive statistics specifically counts and percentages of device or procedure related adverse events captured through 6 months post-surgery will be summarized.

6 Statistical Analyses

6.1 General Considerations

Except where otherwise specified, the following general principles apply to the planned statistical analyses. All statistical analysis will be conducted using SAS version 9.4 or later (SAS Institute Inc., Cary, NC) or other widely accepted statistical or graphical software as required.

6.1.1 Descriptive Statistics

Continuous data will be summarized with mean, standard deviation, median, minimum, maximum, and number of evaluable observations. Categorical variables will be summarized with frequency counts and percentages. Confidence intervals may be presented, where appropriate, using the t-distribution for continuous data and Clopper-Pearson Exact method for categorical variables.

Statistical Analysis Plan		Page 9 of 13
Sponsor Cochlear Americas	Study A post-market interventional cohort study evaluating the clinical efficacy of the Osia 2 system in the US Market	Version 3.0

6.1.2 Visit Windows

Visit windows and the schedule of study assessments are found in the CIP Section 3.

Unless otherwise specified, visit based assessments will be analyzed for each analysis time point according to the nominal visit entered in the Case Report Form (CRF) regardless if it is out of window.

6.1.3 Statistical Significance

Hypothesis testing will be performed at the one-sided 0.025 significance level.

6.2 Analysis Populations

The following analysis populations are defined for analysis:

1. The ITT analysis cohort is defined as all implanted.

Analysis will be based on the intent-to-treat population. In order to obtain a complete ITT population, multiple imputation will be used for any missing outcome data.

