8.2.2 Additional Risks Associated with Implantation of the Study Device

- Pain or discomfort
- Skin irritation near the implant, swelling or redness near the magnet site, skin breakdown
- Sense of numbness or stiffness in the area of the surgery
- Failure of the implant to properly anchor to the skull-bone due to a lack of adequate bone quantity/quality, trauma, infection, generalized diseases and surgical complications
- Other medical complications that may require additional medical treatment, such as:
 - Concurrent CSF leakage: a leak of CSF (cerebrospinal fluid) through the hole in the skull
 - Subdural injury: blood vessels near the brain may burst
 - Subcutaneous hematoma: bruises and contusions on the skin
 - Skin-flap infection, irritation or inflammation
 - Extrusion of the device caused by a foreign body under the skin
 - Revision surgery to remove the study implant in the event of device failure
- Failure of the implant or sound processor could result in the perception of an uncomfortably loud sound sensation, intermittent sound, or no sound.
- The implanted magnet may affect MRI (Magnetic Resonance Imaging) procedures. The magnet may influence the MRI scanner or the ability of the scanner to detect certain changes. Under certain circumstances removal of the AMDT may be necessary prior to MRI scanning.
- There may be side effects that are not known at this time.

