9.4 Sample Size Determination

The planned sample size of 20 will provide greater than 95% power under a conservatively assumed mean of 12 and standard deviation of 15. Calculations are based on a one-sided 0.025 alpha and include allowance for attrition of up to 20%.

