9.5 Analysis Populations

Analysis will be based on the intent-to-treat population. In order to obtain a complete ITT population, multiple imputation will be used for any missing outcome data.

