17 SUSPENSION OR PREMATURE TERMINATION

The Sponsor will discontinue the clinical investigation site if:

- 1) major non-adherence to the CIP or GCP principles is occurring
- 2) it is anticipated that the subject recruitment will not be adequate to meet the objectives of the clinical investigation

An ongoing clinical investigation may be discontinued in case of:

- 1) device failure
- 2) serious or intolerable ADE, leading to the explant or discontinued use of the device
- 3) subject's death

In the event of premature study termination, the subjects will continue to be managed clinically by their medical provider.

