6.6.1.2 Handling of Missing Data

In the event there are missing primary endpoint data the primary endpoint will be analyzed using a multiple imputation analysis. SAS PROC MI will be used to produce 100 imputed datasets. The imputed variable will be the difference between aided and unaided conditions at 3 months in the change in adaptive speech in noise test from preoperative. The following variables will be used as predictors in the model:

- Age
- Sex
- Pre-operative unaided adaptive speech in noise test

The estimates for the mean difference between aided and unaided change from pre-implant will be combined using PROC MIANALYZE providing an overall estimate for the primary endpoint, 95% confidence interval and one-sided p-value.

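### An implant explanted or permanently failed before Month 3 is either imputed as if it worked or dropped from the primary analysis, and no planned analysis counts it as no benefit

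*SAP*

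**What the plan says.** SAP 6.2 makes the intent-to-treat cohort all implanted subjects and adds: "In order to obtain a complete ITT population, multiple imputation will be used for any missing outcome data". Protocol 9.5 has the same rule: "multiple imputation will be used for any missing outcome data". Neither sentence distinguishes reasons for missingness.

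SAP 6.6.1.2 gives the method: 100 imputed datasets, with age, sex and preoperative unaided score as predictors. On the target it says: "The imputed variable will be the difference between aided and unaided conditions at 3 months". What is imputed is thus the benefit itself. Device status and reason for missingness are not in the model.

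SAP 6.6.1.1 points elsewhere. It assesses the endpoint in intent-to-treat subjects whose preoperative and 3-month data are both complete.

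The Protocol foresees loss of the device. Its risk list (8.2.2) includes failure to anchor, extrusion, and "Revision surgery to remove the study implant in the event of device failure". Section 17 names, among the grounds for discontinuing the investigation, "serious or intolerable ADE, leading to the explant or discontinued use of the device". Neither place gives a rate.

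Protocol 7.2.6 says that a subject withdrawn for device safety or performance problems is asked to stay in follow-up for adverse events, and that withdrawn treated subjects are not replaced.

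**The concern.** The primary endpoint compares device-on with device-off at Month 3. After explant or permanent implant failure there is no device-on condition to test, so the score is missing because the device failed. The imputation model cannot see that. It is fitted to subjects who were tested with a working device, and it gives the failed subject the benefit expected for that age, sex and baseline.

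Nothing else in the plan corrects this. The only treatment failure that the Protocol describes (Section 14) is a subject who was not successfully implanted, and that subject is outside an all-implanted cohort. SAP 6.8 summarizes failures and discontinuations due to adverse events separately under safety, which leaves the primary estimate as it is. The sensitivity analyses in Protocol 9.6 cover period and crossover effects only.

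At stake is how the number is read. The study is meant to support reimbursement (Protocol 4.2). A mean labelled intent-to-treat in all implanted subjects invites reading as benefit per implanted patient, whereas it would describe benefit given a working device.

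**Working it through.** **Inputs.** N = 20, mean 12, SD 15 and attrition up to 20% (SAP Section 5, Protocol 9.4). One-sided alpha 0.025: "Hypothesis testing will be performed at the one-sided 0.025 significance level" (SAP 6.1.3). The test is a paired t-test (SAP 6.6.1.1). The SAP's alternative puts benefit in the negative direction; 12 is used here as the size of the benefit. The number of failures k is assumed, from 1 to 4 of 20.

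**The plan's own figure.** The SAP states: "The planned sample size of 20 will provide greater than 80% power under a conservatively assumed mean of 12 and standard deviation of 15". With 20% attrition, n = 20 × 0.8 = 16. The noncentrality is (12/15) × √16 = 3.2, and the noncentral t gives power of 84.8%, so the SAP's figure is reproduced. The Protocol, on the same inputs, states: "The planned sample size of 20 will provide greater than 95% power under a conservatively assumed mean of 12 and standard deviation of 15". That is not reproduced: power is 84.8% at n = 16 and 92.4% at n = 20. This is a separate inconsistency, and the point here does not depend on it.

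**Expected mean benefit with k failures.**

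- Multiple imputation: [12(20 − k) + 12k] / 20 = 12.
- Complete data only (SAP 6.6.1.1): 12(20 − k) / (20 − k) = 12.
- Failures counted as no benefit: 12(20 − k) / 20.
- Excess of the planned estimate over the last: 20/(20 − k) − 1.

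| k | Planned (either reading) | Failures as 0 | Excess |
|---|---|---|---|
| 1 | 12 | 11.4 | 5.3% |
| 2 | 12 | 10.8 | 11.1% |
| 3 | 12 | 10.2 | 17.6% |
| 4 | 12 | 9.6 | 25.0% |

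**Does the imputation behave this way?** A simulation of 20 implanted subjects (4,000 runs per k; 100 imputations by regression on age, sex and baseline; assumed correlation of 0.5 between benefit and baseline) gave failed subjects a mean imputed benefit of 11.7 to 12.2. The overall imputed mean was 11.9 to 12.0.

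**Scale against sampling error.** The standard error is 15/√20 = 3.35. One failure moves the mean by 0.6, or 0.6/3.35 = 0.18 standard errors. Four move it by 2.4, or 0.72.

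**Power, same simulation.**

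| k | Failures as 0 | Complete data only | Imputation, standard df | Imputation, small-sample df |
|---|---|---|---|---|
| 1 | 90.5% | 90.5% | 92.5% | 89.8% |
| 2 | 88.7% | 88.7% | 90.7% | 87.7% |
| 3 | 86.7% | 86.9% | 88.6% | 84.9% |
| 4 | 85.0% | 85.1% | 86.0% | 80.9% |

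The SAP does not say which degrees of freedom apply. Zero scoring lies between the two imputation columns in every row. The zeros lower the mean but also reduce the spread.

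**The case against.** The strongest reply is that the test asks whether the device helps when it is on, and that for this question a working-device estimate is legitimate. Scoring a failure as 0 is then a choice of estimand and not a known fact. This stands, and it is why zero scoring belongs in a sensitivity analysis and need not replace the primary rule. It does not answer the label: if the working-device quantity is intended, the SAP should say so, and a cohort defined as all implanted suggests otherwise.

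A reader might go further and infer that anyone who stops using the device is imputed. The documents do not support that. Visit 5 includes an aided test with the Osia processor (Protocol Section 3 and 7.3.2.7.4), so a non-user who attends with a functioning implant can be tested, and that score is observed. Likewise, a faulty processor can be repaired or returned through the commercial process (Protocol Section 12), and SAP 6.1.2 keeps a late score under its nominal visit. Only explant or permanent implant failure rules out an aided test.

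It is also fair to say that no sentence directs explants to be imputed. The result follows from a rule covering any missing outcome, together with silence about device loss.

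**Conclusion.** The point holds for explant and permanent implant failure before Month 3. Under SAP 6.2 and 6.6.1.2 such a subject is credited with about the average benefit; under SAP 6.6.1.1 the subject disappears. Both give an estimate of benefit with a working device.

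On the plan's mean of 12 and N = 20, the estimate would be about 5% (one failure) or 11% (two failures) above the figure with failures counted as no benefit. These sizes rest on an assumed number of failures, on the zero score, and on failures being otherwise like the other subjects. If no implant is lost before Month 3, there is no effect.

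Two stronger conclusions are not supported. The 25% figure needs four failures in 20. That would turn the whole attrition allowance into device failure, although the withdrawal reasons in Protocol 7.2.6 also include loss to follow-up and withdrawn consent. Nor is the superiority conclusion in danger from this source: power hardly changes, and the effect is on the size of the benefit.

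**What to change.** 1. Reconcile SAP 6.6.1.1 with 6.2 and 6.6.1.2, so that one statement says whether subjects without a Month 3 score are imputed or excluded in the primary analysis.
2. Add to SAP 6.6.1.2 a named sensitivity analysis, reported beside the primary result. For subjects who cannot be tested aided at Month 3 because of explant or permanent implant failure, set the aided-minus-unaided difference to 0.
3. In that analysis keep multiple imputation for all other missing data, such as missed visits and loss to follow-up. Use the observed aided score of every subject tested at Visit 5, including non-users and those with a repaired processor.
4. Report the number of subjects in each category.

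The cost is SAP wording and one derived variable. The derivation needs some care: the withdrawal reasons include adverse event and device deficiency but not explant, so failure status has to be assembled from the adverse event form (which records action taken), the device deficiency form and the withdrawal form. The only other downside is a slightly less favourable supporting estimate if failures occur.

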6.3 Handling of Missing Data

Missing primary endpoint data will be imputed via multiple imputation analyses.

All attempts will be made to limit the amount of missing data. Unless otherwise specified, no attempt will be made to impute missing data. If a data point is missing, that data point will not contribute to that portion of the analysis. The number of evaluable observations will be reported in analysis so that extent of missing data can be assessed.

In the case of partial adverse event onset date or date of death, the unknown portion of the date of the event will be imputed. If the month and year are known, the 15th of the month will be used for analysis. If only the year is known, the event will be analyzed as if it occurred on June 30th of the known year. In the rare case that the date is fully unknown, the date will be imputed as the procedure date. Imputation of partial dates is subject to the condition that it must occur on or after the procedure date. In the case where the imputed date is prior to the procedure date, the date of the procedure will be used. As death cannot occur before any documented subject contact, for date of death the imputed date of death must occur on or after last known contact in study.

Statistical Analysis Plan		Page 10 of 13
Sponsor Cochlear Americas	Study A post-market interventional cohort study evaluating the clinical efficacy of the Osia 2 system in the US Market	Version 3.0

6.4 Subject Disposition

The number of subjects will be presented along with reason for any exclusions. Subject accountability will be summarized by visit. The number of subjects who are enrolled, eligible for follow-up, and number completing clinical follow-up will be summarized for each protocol-required visit. In addition, the number of subjects who complete the study or exit early will be summarized by reason.

